Clinical Design	Prospective, international, multi-center, observational, non-randomized study
Clinical Registry Purpose	The aim of this observational post market study is to compile real world outcome data on the use of the CE marked MANTA Vascular Closure Device following percutaneous cardiac or peripheral procedures for large bore (10-18F ID) interventional devices. This study also fulfills EU regulatory requirements for post-market clinical follow-up.
Indications for Use	The 14F MANTA Vascular Closure Device is indicated for closure of femoral arterial access sites following the use of 10-14F devices or sheaths (maximum OD/profile of 18F), and the 18F MANTA Vascular Closure Device is indicated for closure of femoral arterial access sites following the use of 15-18F devices or sheaths (maximum OD/profile of 25F). Procedures include transfemoral TAVI, EVAR and TEVAR; however all participants must meet indications for use and contra-indications as described in the Instructions for Use and sites must adhere to registry requirements.
Device Description	The MANTA device, developed by Essential Medical, Inc., is a VCD intended for use in catheterization laboratories following percutaneous cardiac or peripheral procedures that use the retrograde common femoral artery access route for large bore (10-18F ID) interventional devices. The function of MANTA is to percutaneously close the puncture in the artery wall (arteriotomy) through which the catheters were inserted for the procedure. The closure device consists of a hemostatic plug (collagen) in the tissue tract on the outside of the artery, which is held in place by suture linked to a small molded polymer toggle positioned inside the artery. A tiny stainless steel lock is used to secure the components in a sandwich through and on either side of the arteriotomy.

Protocol Element	Details	
Device Illustration		
Number of Subjects	
Up to 500 patients implanted with MANTA VCD which will consist of 2 cohorts.
 
 • Cohort 1 restricted to TAVI procedures (T Group) - T Group will require CT at baseline and femoral angiogram post-MANTA deployment. • Cohort 2 includes all other on-label CE-marked medical devices in accordance with MANTA device IFU excluding TAVI procedures (NT Group) - such as mechanical circulatory support (MCS), EVAR and TEVAR procedures. ET Group does not require MSCT at baseline or invasive angiography post-MANTA deployment. 	
Location of Sites	
Experienced sites in EU and Canada currently implanting the MANTA VCD, signed off by local MANTA distributors or Sponsor
 
Geography may include: Switzerland, Netherlands, Finland, Denmark, Sweden, Norway, Canada and the United States with any sites that meet the experience and interest requirement. The registry may include up to 20 participating sites.
	
User Experience	
Individual operators with 10 or greater MANTA implants signed off by local distributors or Sponsor.
	
Duration of the Registry	
Approximately 6-18 months for enrollment. A subset of 100-120 patients will undergo follow-up at 12M post-procedure. Approximately 36 months for entire duration of study.
	
Device	
14F and 18F MANTA Vascular Closure Devices
	
Primary Objectives	
1. Major and Minor access site related Complications (as described below): within 30 days of procedure. Adapted from the VARC-2 definitions ¹:
 
Major femoral vascular complications: Femoral access site or access-related vascular injury (dissection, stenosis, perforation, rupture, arterio-venous fistula, pseudoaneurysm, hematoma, irreversible nerve injury, compartment syndrome, percutaneous closure device failure) leading to death, life-threatening or major bleeding; OR, downstream distal embolization (lower extremities) requiring surgery or resulting in amputation; OR, the use of unplanned endovascular or surgical intervention associated with death, major femoral bleeding; OR, any new ipsilateral lower extremity ischemia documented by patient symptoms, physical exam, and/or decreased
	

¹ Kappetein AP, Head SJ, Génereux P et al. Updated standardized endpoint definitions for transcatheter aortic valve implantation: The Valve Academic Research Consortium-2 consensus document. J Thorac Cardiovasc Surg

2013;145:6-23.

Protocol Element	Details
	
or absent blood flow on lower extremity angiogram; OR, surgery for femoral access site-related nerve injury; OR, permanent femoral access site-related nerve injury.
 
Minor femoral vascular complications:
 
Access site or access-related vascular injury (dissection, stenosis, perforation, rupture, arterio-venous fistula, pseudoaneuysms, hematomas, percutaneous closure device failure) not leading to death, life-threatening or major bleeding; OR, downstream distal embolization (lower extremities) treated with embolectomy and/or thrombectomy and not resulting in amputation; OR, any unplanned endovascular stenting or unplanned surgical intervention not meeting the criteria for a major vascular complication; OR, vascular repair or the need for vascular repair (via surgery, ultrasound-guided compression, transcatheter embolization, or stent-graft); OR, percutaneous closure device failure*.
 
*Failure of a closure device to achieve hemostasis at the arteriotomy site leading to alternative treatment (other than manual compression or adjunctive endovascular ballooning).
 
2. Time to Hemostasis: The elapsed time between MANTA deployment (withdrawal of sheath from artery) and first observed and confirmed arterial hemostasis (no or minimal subcutaneous oozing and the absence of expanding or developing hematoma).

Clinical Visits/Testing	
 ▪ Baseline evaluation: Informed consent, history and physical, CT Angiographic Scan ▪ Index Procedure: Adverse Events ▪ Pre-MANTA Closure Procedure: Target Femoral Access Site Visual Assessment ▪ MANTA Closure Procedure: ACT/Systolic Blood Pressure ▪ Post-MANTA Closure Procedure: Femoral Angiography, Target Femoral Access Site Visual Assessment, Time to Hemostasis, Adverse Events ▪ Post procedure: Target Femoral Access Site Visual Assessment, Adverse Events ▪ Discharge: Target Femoral Access Site Visual Assessment, Time to Ambulation, Adverse Events ▪ 30D (+/- 7 days): Clinical Exam, Target Femoral Access Site Visual Assessment, Adverse Events 
 • 30 Day Follow-Up may be done via phone if not SOC/ per site SOC timing (6 weeks) ▪ 12M (+/- 30 days): Clinical Exam, Target Femoral Access Site Visual Assessment, Adverse Events (subset only)
Indications	
 1. The 14F MANTA is indicated for closure of femoral arterial access sites following the use of 10-14F devices or sheaths (maximum OD/profile of 18F) 2. The 18F MANTA device is indicated for closure of femoral arterial access sites following the use of 15-18F devices or sheaths (maximum OD/profile of 25F).

Contraindications	
1. Severe calcification of the access vessel.2. Severe peripheral artery disease.3. Puncture in the origin of the profunda femoral artery.4. Sheath insertion in vessel other than the femoral artery.5. Marked tortuosity of the femoral or iliac artery.6. Marked obesity or Cachexia (BMI >40 or <20).7. Blood pressure > 180 mmHg.
-------------------	---

Protocol Element	Details
Statistical Analysis:	Statistical analysis will consist of descriptive statistics using standard methods, such as mean, standard deviation, minimum/maximum, proportions, counts, etc. Data will be qualitatively compared to VARC-2 endpoints in the literature.

Schedule of Assessments

Assessment/ Interval	Screening Visit	Index Proced- ure	MANTA Procedure			Post- Proced- ure	Hospital Discharge	Follow-Up	
			Pre- MANTA Closure	MANTA Closure	Post- MANTA Closure			30D Follow-up (+7 days)	12M ⁵ Follow- (± 30 D)
Subject Eligibility/Informed Consent	X								
Medical History	X								
Medication	X ¹	X ¹	X ¹	X ¹	X ¹	X ¹	X ¹	X ¹	X ¹
CT Angiographic Scan	X ^{2*}								
ACT/Systolic Blood Pressure				X ³					
Femoral Angiography		X			X ^{4*}				
Target Femoral Access Site Assessment			X		X	X	X	X	X
Time to Hemostasis					X				
Time to Ambulation							X		
Adverse Events		X	X	X	X	X	X	X	X

1. Medications (only Aspirin, Clopidogrel, Vitamin K Antagonists and, NOAC's: [eloxaban, rivaroxaban, dabigatran, apixaban] will be collected)
2. Screening Visit CT Scan to assess both limbs for presence/absence of calcium, atherosclerotic disease, tortuosity, and acceptable flow rates.
3. Prior to MANTA closure, record ACT and systolic BP (per contraindications BP<180; recommend ACT below 250 seconds prior to closure)
4. Post-MANTA closure, perform target (ipsilateral) common femoral angiography from contralateral access site to ensure patency into the ipsilateral common femoral artery
 - * #2 CT Angiographic Scan and #4 Post MANTA femoral angiogram are required in cohort 1
5. A subset of study enrollment, 100-120 subjects at up to 7 sites, will complete the 12M follow-up visit.

Abbreviations/Acronyms

Abbreviation/ Acronym	Definition
ACT	Activated clotting time
ADE	Adverse device effect
AE	Adverse event
BAV	Balloon aortic valvuloplasty
BMI	Body mass index
CA	Competent authority
CAC	Clinical acceptance criterion/criteria
CE	Conformité Européene (European Conformity)
CEC	Clinical events committee
CFR	(U.S.) Code of Federal Regulations
CRF	Case report form
CRO	Contract research organization
CTA	Computed tomography angiography
DMP	Data management plan
EC	Ethics committee
CRF	Case report form
EU	European Union
EVAR	Endovascular aneurysm repair
F	French (1F = 0.33 mm); used for defining catheter size
FDA	U.S. Food & Drug Administration
FIH	First in human
ID	Inner diameter
INR	International normalized ratio
IRB	Institutional review board
ISO	International Organization for Standardization

MCS	Mechanical Circulatory Support
NT Group	Non-TAVI Cohort
OD	Outer diameter
PG	Performance goal
PMA	Pre-market approval
SAE	Serious adverse event
SADE	Serious adverse device effect
SOC	Standard of care
SOPs	Standard operating procedures
T Group	TAVI Only Cohort
TAVR/TAVI	Transcatheter aortic valve replacement / transcatheter aortic valve implantation
TTA	Time to ambulation
TTH	Time to hemostasis
UADE	Unanticipated adverse device effect
USADE	Unanticipated serious adverse device effect
VARC	Valve Academic Research Consortium
VCD	Vascular closure device

Revision History

Version	Date	Summary of Changes/ Affected Sections
A	14 Nov 2017	Initial Release
B	13 Aug 2019	
• Include 12M follow-up visit for 100-120 out of the 500 total enrolled subjects.• 30D follow-up window clarification per site SOC• Include site selection criteria for 12M visit and minimization of bias• Updated study duration timeline• Updated Schedule of Assessments to include 12M follow-up procedures• Clarified definition of adverse event (AE)• Clarified AE adjudication for 12M• General administrative updates
C	26 Sep 2019	
• Updated study duration timeline and location of sites• Included Canadian sites to site selection criteria for 12M visit• Updated number of sites criteria for 12M visit• Clarified adverse event (AE)/ serious adverse event (SAE) terminology under reporting SAE/AE for this study• General administrative updates

Table of Contents

Protocol Signature Page	2
Protocol Synopsis	3
Schedule of Assessments	7
Abbreviations/Acronyms	8
Revision History	10
Table of Contents.....	11
1. Introduction	14

1.1 Large Bore Vascular Interventions

Closure of large bore (10-24F) arteriotomies after interventional procedures (e.g., transcatheter aortic valve replacement, endovascular aneurysm repair, implantation of a percutaneous left ventricular assist device, etc.) continues to be problematic. Once the procedure has been completed, the physician must close and obtain hemostasis at the puncture, which is in a high- pressure artery and may be as large as 8mm in diameter. Currently, this is accomplished by manual compression at the lower end of this size range (typically <12F) or surgical access/repair or use of suture-mediated VCDs at the higher end of sheath sizes (above 12F). Consequently, the vascular complication rates for procedures utilizing large bore sheaths have been reported at up to 20%. [1]

1.2 MANTA Large Bore Vascular Closure Device

The MANTA VCD is innovative in that it is specifically designed to close large bore (10-18F) punctures following percutaneous transcatheter cardiac and peripheral interventions. The MANTA design utilizes the foundation of the existing smaller bore Angio-Seal and X-Seal “tethered collagen plug” design of closure devices (i.e., the resorbable anchor and collagen plug) and builds on that foundation with innovations to specifically address the larger bore requirements. This includes holding the anchor within a separate release tube until it is safe to deploy the anchor close to the artery wall puncture; this prevents the anchor from deploying too far within the artery, catching across the artery and potentially deploying collagen into the vessel. A lever on the deployment handle actively deploys the anchor at the appropriate time and position.

[figure not shown]

Figure 1: Illustration of the MANTA Vascular Closure Device

1.3 Pre-clinical Investigation Results

Extensive preclinical testing, including bench, animal and biocompatibility testing, has been completed on the MANTA devices. This testing has demonstrated that the MANTA device is safe and performs as intended by the manufacturer. The bench testing demonstrated that the MANTA device meets its design inputs. Biocompatibility testing demonstrated that the materials

used in the MANTA device are biocompatible. The extensive animal testing demonstrated that the MANTA devices, both 14F and 18F, perform as intended in the exposed aorta of an animal model and that the devices, particularly the intra-arterial toggle, encapsulate and resorb as expected without adverse tissue reactions.

This was a prospective, non-randomized, multi-site, non-blinded study to evaluate the safety and performance of the 14F and 18F MANTA Vascular Closure Devices at 3 sites, one in Italy and two in the Netherlands. The study was conducted to generate data to support a CE mark in the EU. Fifty (50) subjects were enrolled and treated with the MANTA device. The synopsis of the final clinical study report is excerpted here in abbreviated form:

Study objectives

In this prospective, multi-center, open-label, single-arm clinical investigation '*Clinical Study to Evaluate the Safety and Performance of MANTA Vascular Closure Device*' the safety and

performance of the MANTA VCD in subjects who had undergone interventional procedures using a 10F to 18F procedural sheath were evaluated. Specifically, the primary safety endpoint was assessed by evaluation of access site related Major Complications in comparison to published literature on hemostasis techniques for closing large bore punctures (primarily, surgical closure and suture-mediated percutaneous closure [i.e., single or multiple Proglide/Prostar devices]). The primary performance endpoint was assessed by Hemostasis Success. Secondary objectives were to evaluate the Minor Complications, Time to Hemostasis, Time to Ambulation, and Treatment Success.

Results

The study population consisted of subjects who were candidates for non-emergent transcatheter interventional procedures via a 10-18F femoral sheath (e.g., TAVR, BAV, EVAR). Treated subjects were followed for 60 days post-procedure.

In total, 50 subjects were treated at 3 centers in Europe. The first subject was enrolled on 22 July 2015 and the last subject was enrolled on 27 January 2016. The first subject out was on 7 October 2015 and the last subject out was on 22 March 2016. Sixteen (16) subjects were treated with the 14F MANTA device (32%) and 34 were treated with the 18F MANTA device (68%). Of the enrolled subjects, 23 subjects were male (46%) and 27 were female (54%). Mean age was 79.5 ± 8.3 years, mean weight was 75.4 ± 15.6 kg, mean height was 164.1 ± 10.0 cm, and mean Body Mass Index was 27.8 ± 4.4 kg/m².

Primary Safety Endpoint

The primary safety endpoint was to evaluate the percentage of patients with one or more Major Complications reported from the procedure until the first study visit (30 ± 7 days following procedure). Three (3) Major Complications were reported in 3 subjects (6%). A non-inferiority test comparing these results with results from the SEVAR (surgical closure) arm as obtained in the PEVAR trial [2], demonstrated strong evidence that rate of Major complications was non-inferior to the published SEVAR results ($p < 0.05$).

Primary Performance Endpoint

The primary performance endpoint was to evaluate the percentage of patients with Hemostasis Success. Hemostasis Success was achieved in 47 subjects (94.0%). For the 3 subjects that did not reach Hemostasis Success, hemostasis was obtained in 37, 27 and 13 minutes and manual pressure was required for 6-11 minutes.

Secondary Safety Endpoint

The secondary safety endpoint was to evaluate the percentage of patients with one or more Minor Complications reported from the procedure until the first study visit (30 ± 7 days following procedure). Five (5) Minor Complications were reported in 5 subjects (10%).

Secondary Performance Endpoints

The secondary performance endpoint Time to Hemostasis was to evaluate the elapsed time between MANTA deployment and the first observed and confirmed arterial hemostasis. Mean

Time to Hemostasis was 2 minutes and 23 seconds (Standard deviation: 6 minutes and 38 seconds; Median: 24 seconds; Minimum: 2 seconds; Maximum: 37 minutes and 10 seconds). For 37 subjects (74%), Time to Hemostasis was reported as \leq 1 minute; for 10 subjects (20%), 1 to 10 minutes were required until hemostasis was achieved; and for 3 subjects (6%), more than 10 minutes and manual pressure were required until hemostasis achievement

The secondary performance endpoint Time to Ambulation was to evaluate the elapsed time between MANTA deployment and when ambulation is achieved. Mean Time to Ambulation was 44 hours and 10 minutes (Standard deviation: 25 hours and 7 minutes; Median: 43 hours and 34 minutes; Minimum: 3 hours and 42 minutes; Maximum: 142 hours and 1 minute). For 5 subjects (10%), Time to Ambulation was reported as less than 24 hours; for 28 subjects (56%) Time to Ambulation was between 24 and 72 hours; and for 6 subjects (12%) more than 72 hours were required until ambulation. Hemostasis was maintained during ambulation for all subjects with available data (n=41).

The secondary performance endpoint Treatment Success was to evaluate the number of subjects that had Hemostasis Success and no Major Complications reported. Treatment Success was achieved in 47 subjects (94%). Absence of Hemostasis Success, as well as presence of one or more Major Complications, occurred in the same 3 subjects.

Safety Assessment

All adverse events (AEs) that were reported were assessed for type, severity, and device or procedure relatedness. In total, 101 AEs were reported during the course of the study, involving 45 subjects (90%). Forty-six (46, 45.5%) of these events were classified as 'not related' to the device. Of the 101 reported AEs, 25 were classified as 'serious'. Twenty-two (22, 88.0%) of these serious events were classified as 'not related' to the device. None of the AEs nor any of the SAEs were unanticipated.

The most common reported AE concerned a hematoma at the access site, which was reported 29 times (in 58% of the subjects) (10 times (20%) hematoma $>$ 6 cm; 19 times (38%) hematoma \leq 6 cm). One (1) of these hematomas was classified as 'moderate' severity, all others were classified as 'mild'.

Femoral artery stenosis was reported in 17 cases (34%). Although all events were reported as possible (2 cases, 4%) or definite (15 cases, 30%) related to the device, all events were classified as 'mild' severity and none of these femoral artery stenosis required intervention.

Twenty-five (25) AEs were classified as 'serious', involving 20 subjects (40%), of which 3 were probably or definitely device related (2 excessive access site bleedings; 1 pseudoaneurysm). All 3 events were classified as Major Complications.

During the course of the study, 4 subjects died. One (1) subject suffered from renal insufficiency and infection (cause unknown); another subject suffered from a cerebrovascular accident; 1 subject suffered from intestinal perforation; and the fourth subject suffered from a systemic infection. None of these events was considered related to the device nor to the procedure.

There were no unanticipated serious adverse device effects reported for any of the subjects.

Discussion

Safety

The 3 Major Complications reported were the only safety events that were classified as potentially or definitely device-related SAEs. For 2 of these events the Sponsor concluded that these events were a result of minor manufacturing deficiencies. Necessary corrective action has been taken to improve the manufacturing process and limit the associated safety risk.

In total, 10 AEs described an access site related hematoma > 6 cm. The investigator who treated these subjects, confirmed that this concerned an ecchymosis in 5 cases (50%), which is sometimes difficult to distinguish from a hematoma. This information was accompanied by ultrasound data in 3 cases, where the hematoma at the artery was assessed as 0.96, 2.28 and 0.82 cm². The 5 remaining cases concerned true hematomas based on visual assessment and available ultrasound data and those were classified as Minor Complications. No other Minor Complications were reported during the course of the study.

The AE termed 'stenosis at the access site' has only been reported at site 01. The observed difference in frequency proportion may be due to an interest bias. The involvement of an independent interpreter, e.g. by use of a qualified core lab, would limit the interpretation bias in future studies.

A large number of unrelated AEs can be anticipated with a study population as included in this study, with a mean age of 79.5 years (Standard deviation: 8.3 years; Median 80.7 years; Minimum 42.6 years; Maximum 90.4 years) and who are undergoing a significant intervention. Additionally, physical exam at baseline revealed that 46 subjects (92%) were suffering from one or more comorbid conditions prior to MANTA treatment.

Performance

Hemostasis Success was obtained in 94% of the subjects. The mean Time to Hemostasis reported in this study was 2 minutes and 23 seconds. The minimum reported Time to Hemostasis was 2 seconds and 74% of the subjects had a time to hemostasis reported that was less than 1 minute. These results indicate excellent performance of the device, given that the MANTA device is used for vascular closure of very large punctures. Outer diameters of the index procedure sheaths which the 18F MANTA device closed were as large as 24.5F (8.17 mm).

The subjects for whom no Hemostasis Success was obtained (n=3, 6%) were the same subjects for whom a Major Complication was reported, as well as for whom a Time to Hemostasis of more than 10 minutes was reported.

Conclusion

Results from this study demonstrate the excellent performance of the MANTA closure device in achieving hemostasis in 94% of the treated subjects, with 74% achieving hemostasis within 1 minute in patients that underwent percutaneous transcatheter interventional procedures using a 10-18F procedure sheath. Three (3) Major Complications were reported (two (2) of which were associated with minor manufacturing issues that have been corrected), accounting for 6%

of the treated population, demonstrating strong evidence that the proportion of MANTA subjects with Major complications were non-inferior to those of the SEVAR trial ($p<0.05$).

In conclusion, the results of this study demonstrate that the MANTA vascular closure device is safe and performs as intended by the Sponsor.

Pivotal Clinical Study to Evaluate the Safety and Effectiveness of MANTA Vascular Closure Device:

The purpose of this study is to demonstrate the safety and effectiveness of MANTA in achieving hemostasis in femoral arterial access sites in subjects undergoing percutaneous transcatheter interventional procedures using a large-bore procedure sheath for purposes of obtaining a PMA approval in the U.S. The study will evaluate times to hemostasis and ambulation, technical success, ambulation success, treatment success, procedure time, and the rate of access-site-related complications; the primary endpoints will be compared to Performance Goals (PG) derived from published literature and the clinical judgment of expert advisors. A total of 341 subjects were enrolled in the study and follow-up is now complete. Study was closed in December 2017. The study met its endpoints. U.S. PMA approval for the MANTA device was received, on the basis of this Pivotal Study, in February 2019.

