7.8 Sponsor Representatives

Trained Sponsor personnel may perform certain study activities to ensure compliance to the clinical protocol and may provide technical expertise. Monitoring may be performed by Essential Medical and/or authorized designees according to the International Organization for Standardization (ISO) 14155 and MEDDEV guidelines for post market studies; and applicable Essential Medical standard operating procedures and work instructions. Qualified monitors will ensure investigators comply with this clinical protocol and ISO 14155 and MEDDEV post market requirements.

To ensure study personnel accept, understand and complete their assigned responsibilities, monitors, or field clinical personnel may perform periodic site visits during the course of the study. These actions will help to ensure the continued acceptability of the facilities, compliance to the clinical protocol and relevant regulations, and the maintenance of complete records.

Monitoring will include review and resolution of missing or inconsistent results and source document verification (i.e. comparison of submitted study results to original reports) to assure the accuracy of the reported data.

8. Statistical Methods

8.1. *Study Hypothesis*

This is a single arm study, and no formal hypothesis will be tested.

8.2. *Sample Size Considerations*

Up to 500 subjects are considered a meaningful sample size to assess real-world use of the MANTA device. There is no statistical basis for the sample size.

8.3. *Data Analysis*

8.3.1 *Endpoints*

The following Performance Endpoints will be evaluated for the MANTA device, definitions are provided in Section 4:

1. Time to Hemostasis (Primary)

The following Safety Endpoints will be evaluated for the MANTA device, definitions are provided in Section 4:

1. The percentage of patients with one or more VARC-2 Major femoral vascular complications within 30 ± 7 days following procedure (Primary)
2. The percentage of patients with one or more VARC-2 Minor femoral vascular complications within 30 ± 7 days following procedure (Secondary)

8.3.2 *Final Analysis*

Statistical analysis will consist of descriptive statistics using standard methods, such as mean, standard deviation, minimum/maximum, proportions, counts, etc. Two-sided 95% confidence

intervals will be calculated, when relevant. Comparison to published literature results will be descriptive only; there will be no comparative statistics.

8.4. *Interim Analysis*

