## 5 Statistical Analyses and Study Objectives

Statistical analyses will consist of descriptive statistics mean, standard deviation, median, minimum/maximum and 95% confidence intervals for continuous data and counts, proportions and 95%

confidence intervals for categorical data. Data will be qualitatively compared to VARC-2 endpoints in the literature.

All subjects with an attempted procedure where femoral artery access was initiated and MANTA device was attempted will be included in the performance and safety measures. The performance and safety endpoints will be summarized for the overall population, by cohort (TAVR vs not TAVR), and by MANTA device size (14 or 18 Fr) at a minimum. The 12M safety endpoint will also be summarized for the 12M cohort.

At the time this SAP was drafted, enrollment has closed, but follow-ups are still being completed. One subject had both sides (left and right femoral arteries) used for procedures of all enrolled subjects so summaries may be either patient based (number of participants) or device based (number of participants + 1).

The protocol specified that results will be compared to values observed in the literature. This comparison can be made by comparing the 95% confidence intervals to rates from literature. If the rate is within the 95% confidence interval, the prespecified intention is to report that a difference between the prior literature reported rate and the MARVEL study's observed rate has not been demonstrated. At a minimum, the results will be compared to the observed rates from the 2 pre-market trials, the EU Pre-Market Clinical Study (Netherlands and Italy, N=50) and the U.S. Pivotal trial (N=263 primary analysis cohort).

**Table 2.** Rates from pre-market trials for MANTA device

Trial	Time to Hemostasis (min) Mean $\pm$ SD, Median, Range, upper 97.5% confidence bound	Major Complication Rate (%) percent, 97.5% upper confidence bound	Major VARC-2 Complication Rate (%) percent	Minor Complication Rate (%) percent
EU Pre-market study (N=50)	2.38 $\pm$ 6.63 0.4 Range: 0, 37 97.5% UCB = N/A	3/50 (6%)	1/50 (2%)	0/50 (0%)
FDA PMA results (N=263)	1.09 $\pm$ 2.63 0.4 97.5% UCB = 1.41	5.3% 97.5% UCB = 8.8%	4.2%	2.7%

Additional VARC-2 complication rates have been pulled from the literature and are summarized in Table 3 below.

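### The EU pre-market study's minor complication rate is 10% (5/50) in the protocol but 0% (0/50) in SAP Table 2, where it serves as a comparator

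*Protocol*

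**What the plan says.** Protocol 1.4 summarises the EU pre-market study (50 treated subjects, three sites). Under its secondary safety endpoint, for the period up to the first visit at 30 ± 7 days, it reports: "Five (5) Minor Complications were reported in 5 subjects (10" per cent). The discussion says what these were: "The 5 remaining cases concerned true hematomas based on visual assessment and available ultrasound data and those were classified as Minor Complications". It adds: "No other Minor Complications were reported during the course of the study". The summary describes itself as shortened: "The synopsis of the final clinical study report is excerpted here in abbreviated form".

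SAP section 5, Table 2 lists the same study (N=50) with three complication cells: major 3/50 (6%), major under VARC-2 1/50 (2%), and minor 0/50 (0%). The table separates a plain major column from a VARC-2 major column. Its single minor column carries no VARC-2 label in the text as read, and no note or source explains the zero. The sentence after the table begins "Additional VARC-2 complication rates have been pulled from the literature".

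The SAP puts the table to use: "At a minimum, the results will be compared to the observed rates from the 2 pre-market trials". It also sets a reporting rule: "If the rate is within the 95% confidence interval, the prespecified intention is to report that a difference" has not been demonstrated. Protocol 8.3.2 limits the status of such comparisons: "Comparison to published literature results will be descriptive only".

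**The concern.** Two current texts give different counts for what appears to be the same quantity in the same 50 people. The protocol leaves no room for a different total under the study's own definition, since it names the five events and rules out others. A reader of Table 2 would take 0/50 as the minor complication rate of the EU study.

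At stake is what the final report says when it sets MARVEL's minor rate beside this study. Against 0%, any minor complication at all makes MARVEL look worse than the pre-market experience. Against 10%, a rate of a few per cent makes it look better.

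**Working it through.** **Inputs.** EU study counts: Protocol 1.4. Comparator cells and the confidence interval rule: SAP section 5 and Table 2. MARVEL size: up to 500 (SAP section 4). The SAP does not name an interval method for proportions, so exact (Clopper-Pearson) 95% intervals are assumed.

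**Step 1: do the other EU cells in Table 2 reproduce?**

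| Cell | Protocol 1.4 | Converted | Table 2 |
|---|---|---|---|
| Mean time to hemostasis | 2 min 23 s | 2 + 23/60 = 2.38 min | 2.38 |
| SD | 6 min 38 s | 6 + 38/60 = 6.63 min | 6.63 |
| Median | 24 s | 24/60 = 0.40 min | 0.4 |
| Maximum | 37 min 10 s | 37.2 min | 37 |
| Major complications | 3 of 50 | 6% | 3/50 (6%) |
| Minor complications | 5 of 50 | 10% | **0/50 (0%)** |

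Only the minor cell disagrees. The VARC-2 major cell (1/50) cannot be checked, because the protocol gives no VARC-2 count for that study.

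**Step 2: how far apart are the two figures?** The exact interval has lower limit Beta(0.025; x, n−x+1) and upper limit Beta(0.975; x+1, n−x).

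- 5/50 = 10%: 3.3% to 21.8%
- 0/50 = 0%: 0% to 7.1%

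**Step 3: could leaving out patients with a major complication explain the zero?** SAP 5.3 counts a minor complication only in patients without a VARC-2 major one. The protocol reports minor complications in 5 subjects and major ones in 3, and does not say whether they overlap. Even with complete overlap, 5 − 3 = 2 subjects (2/50 = 4%) had a minor complication only. That rule alone cannot give 0/50. Some events must have been reclassified, or the cell is wrong.

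**Step 4: apply the SAP rule.** For each possible MARVEL count out of 500, ask whether the exact interval contains 0% or 10%.

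| MARVEL events | Observed rate | Exact 95% CI | 0% inside? | 10% inside? |
|---|---|---|---|---|
| 0 | 0% | 0 to 0.74% | yes | no |
| 1 | 0.2% | 0.01 to 1.11% | no | no |
| 30 | 6.0% | 4.08 to 8.45% | no | no |
| 36 | 7.2% | 5.09 to 9.83% | no | no |
| 37 | 7.4% | 5.26 to 10.06% | no | yes |
| 64 | 12.8% | 10.00 to 16.05% | no | yes |
| 65 | 13.0% | 10.18 to 16.27% | no | no |

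The fixed wording therefore depends on the cell at 0 events and at 37 to 64 events. With fewer patients the picture is the same: 10% is inside at 33 to 58 events of 450 (7.3% to 12.9%) and at 29 to 52 of 400 (7.3% to 13.0%), and 0% is inside only at 0 events.

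**Step 5: where might MARVEL fall?** The other MANTA minor rates in SAP Tables 2 and 3 correspond, at 500 patients, to 2.7% × 500 = 13.5, 3.7% × 500 = 18.5, 4.6% × 500 = 23 and 6% × 500 = 30 events. All lie between 1 and 36, where the fixed wording applies to neither figure. There MARVEL's interval would lie wholly above 0% and wholly below 10%. The SAP fixes no wording for a benchmark outside the interval, so reading this as worse or better is an inference about how the report would be understood.

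**The case against.** The strongest answer is that 0/50 is a VARC-2 recount and only a label is missing. It follows a VARC-2 major column in which the count falls from 3 to 1. The next sentence speaks of additional VARC-2 rates, as if Table 2 already held some. SAP 5.2, SAP 5.3 and Table 3 treat both categories as VARC-2. The protocol's synopsis is abbreviated and does not call its minor complications VARC-2. Two counts under two definitions need not conflict, and a shared header may have been lost when the table was read from PDF.

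This is plausible, but neither document says it. A label alone would also leave questions. MARVEL's adapted minor definition lists hematoma, with a threshold above 2 cm confirmed by ultrasound, and the five events came from hematomas reported as larger than 6 cm. Ultrasound confirmation of each of the five is not documented. If two of the three major events (two bleedings and a pseudoaneurysm) were moved out of the major category, the table does not show where they went.

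Two further objections stand. First, 10% is not shown to be like for like with MARVEL either: overlap with the major events is unknown, and the EU study did not count its 19 hematomas of 6 cm or less as minor complications, although some could exceed MARVEL's threshold. Second, the practical effect is limited: the endpoint is secondary in Protocol 5 and 8.3.1, the comparison is descriptive, and the U.S. pivotal trial (2.7%) and the weighted literature rate (11.5%) stand beside this comparator.

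**Conclusion.** The concern holds: the two documents give 10% and 0% for the same study, and the SAP relies on the unexplained 0%. This is a mismatch between documents rather than a failed calculation. The documents do not settle which figure fits MARVEL's minor endpoint; only the EU study report can.

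Under the assumptions of 500 patients and exact intervals, the SAP's fixed wording depends on the cell at 0 events or at 37 to 64 events. At 1 to 36 events, which covers the other MANTA rates in the SAP, the wording is unaffected but MARVEL's position relative to the comparator reverses. From 65 events MARVEL's interval lies above both figures. No hypothesis test, sample size or primary endpoint is affected.

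**What to change.** Before the final report, check the EU minor cell in SAP Table 2 against the EU study report.

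- If 0/50 is an error, replace it with 5/50 (10%; exact 95% CI 3.3% to 21.8%).
- If it is a VARC-2 recount, label the column as VARC-2, state the definition and source, and show the study-defined 5/50 beside it.

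In either case, keep the prespecified comparison and add a sentence on how the comparator's definition differs from MARVEL's, covering the hematoma size threshold and whether patients with a major complication are excluded. The cost is one corrected or labelled table cell and one sentence. No new data are needed and the planned comparison does not change.
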